#### **9.1.1.9 Significant Adverse Events**

Other significant AEs are defined as marked haematological and other laboratory abnormalities (other than those meeting the definition of serious) and any events that led to an intervention, including withdrawal of test drug, dose reduction or significant additional concomitant therapy.

#### **9.1.2 Laboratory Evaluation**

No protocol specific laboratory evaluations will be required other than a urine pregnancy test at screening and at any time during the study if pregnancy is suspected. However, should an abnormal result constituting an adverse event be recorded as part of the patient's standard care, the adverse event shall be recorded in the CRF.

Cell functions, including cytokine production by specific cell population and/or immune activity, and other aspects of the immune response will be analysed as an exploratory endpoint (see Section 8.1.1).

#### **9.1.3 Other Parameters Specific to Study Design**

##### **9.1.3.1 Injection Site Reactions**

Mild or moderate local reactions at the injection site are expected. Patients are likely to experience a skin reaction and some discomfort around the injection site [1]. Each patient will be given general and written advice regarding the management of local injection site reactions and generalised systemic symptoms (e.g., pyrexia, headache and general malaise). Where symptoms persist or result in functional limitations, patients will be advised to attend the next possible research clinic or see their own GP.

Before each administration of IMM-101, the injection site must be inspected for local reaction(s). In addition, patients will be asked to assess their injection site reaction, and its effect on their daily activities:

"Has the local reaction affected your daily activities?"

- Not at all
- Slightly
- Moderately
- Quite badly
- Intolerably

Although a formal assessment is performed before each injection, an injection site reaction may be recorded as an AE at any time if considered appropriate to do so by the Investigator.

In the event of an injection site reaction of Grade 3 (severe) as measured by the NCI CTCAE v4.0 and above, at the discretion of the Investigator, patients may be administered a half dose of the study drug (i.e., a single 0.05 mL intradermal injection of IMM-101) or the time interval between injections of IMM-101 may be extended. Any change in the dose of study drug administered should be recorded in the patient's CRF.

If dosing is discontinued or the patient withdraws from the study as a result of an intolerable injection site reaction, this must be recorded in the CRF.

#### **9.1.3.2 *Pregnancy test***

A urine pregnancy test will be conducted for all females of child-bearing potential during screening and at any other time during the study if pregnancy is suspected (Study Flow Chart of Assessments, Appendix 1).

The result must be negative for the patient to enter or continue in the study.

#### **9.1.3.3 *Prior/Concomitant Medications***

Prior and concomitant medications will be recorded at screening and before the first dose of IMM-101. Prior medications will include all medications taken in the 2 weeks before screening. Patients will be asked if they have taken any concomitant medication at each subsequent visit.

Any changes in concomitant medication since the previous visit will also be recorded on the patient's CRF.

### **9.2 *ASSESSING, RECORDING AND ANALYSING SAFETY PARAMETERS***

Adverse events will be recorded on the patient's CRF from the time of informed consent (i.e., screening). AEs will be followed until 30 days after the end of study/withdrawal. The Investigator may contact the patient by telephone to obtain the information. See Section 0 for further details. Related SAEs will be recorded regardless of time from last dose.

Injection site reactions will be assessed and recorded in the patient's CRF before each injection of study drug. These will only be recorded as an AE if deemed appropriate by the Investigator. In addition, the patient's assessment of the effect of the injection site reaction on their daily activities will be recorded at each visit, as described in Section 9.1.3.1.

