### **6.3 PATIENT WITHDRAWAL CRITERIA**

#### **6.3.1 Removal of Patients from Therapy or Assessment**

The patient will be advised in the ICF that they have the right to withdraw from the study at any time without prejudice, and may be withdrawn at the Investigator's or the Sponsor's discretion at any time.

In the event that the patient drops out of the study or is withdrawn from the study, the withdrawal page in the patient's CRF should be completed. On the withdrawal page the

---

CONFIDENTIAL

Immudon Therapeutics Ltd.  
[name]

Investigator (or designee) should record the date of the withdrawal, the person who initiated withdrawal and the reason for withdrawal.

The following are reasons for patient dropout/withdrawal:

Withdrawn by the Investigator due to:

- Adverse event.
- Protocol violation or non-compliance with the Protocol.
- Intolerable injection site reaction.
- Pregnancy.
- Toxicity.
- Other reasons.

Withdrawal requested by the patient due to:

- An AE for which the Investigator did not consider removal from the study necessary.
- Withdrawal of consent.
- Other.

Other:

- Lost to follow-up.
- Administrative problems.

Reasonable effort should be made to contact any patient lost to follow-up during the course of the study in order to complete assessments and retrieve any outstanding data.

For patients who leave the study or when the study ends, normal standards of care, according to local practice, will continue as necessary. In the case of withdrawal, separate consent will be sought to allow the continued collection on patient status.

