#### **Overall Survival (OS)**

OS is defined as the time from enrolment to death due to any cause. OS will be expressed from time of initial diagnosis, time of enrolment in the Phase 1 study as well as from time of enrolment in this long term follow up study.

Patients without a death date will be censored at the date the patient was last known to be alive.

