### **9.5        *ADVERSE EVENT FOLLOW-UP PROCEDURES***

All SAEs will be followed to resolution. All non-serious AEs will be followed until the event has resolved (disappeared) or until they have stabilised, and the relationship to the study drug is clarified. AEs will be followed until 30 days after the end of study/withdrawal. The Investigator may contact the patient by telephone to obtain the information.

---

CONFIDENTIAL

Immudulon Therapeutics Ltd.  
[name]

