10. ANALYSIS CORRESPONDING TO THE STUDY OBJECTIVES

Overall Survival (OS) is defined as the time from a patient's date of Day 0 until date of death. Patients still alive will be censored at withdrawal from the study or at last known date alive if later (where patients have consented to follow-up for overall survival outcome, after they have withdrawn from the study). If consent has been provided by the patient, the patient's final outcome will be included if death and if alive, the patient will have censored outcome at the date last known to be alive.

Post-study survival status after withdrawal from the study, for any withdrawn patients, will be recorded on a separate Post-study Long Term Survival Status CRF, and these data will be included in the analysis and data listings, as described above.

The patient's death is recorded as the date of study completion on CRF page 18 and if after withdrawal from the study, the date of death recorded on the Post-study CRF.

A patient without a death date will be censored in the analysis at the last date known to be alive providing their consent was obtained. Patients withdrawing from the study without consent for further follow up will be censored for survival at the date of their withdrawal from the study (recorded on CRF page 18).

Overall Survival will be summarised by Kaplan-Meier curves. Median, 25% and 75% survival estimates as well as associated 95% CIs will be reported in Table 8 and Figure 2.

SAS procedure output for the OS analysis will be included as an appendix to the CSR.

The changes in metastatic disease compared with previous assessment (as measured via CT or MRI scan) recorded at the discretion of the investigator, will be presented over the treatment period in data listings only (Listing 11).

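### SAP 10 censors withdrawn patients without post-study consent at withdrawal, so a death recorded in the protocol's post-withdrawal AE follow-up would be left out of overall survival

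*Protocol*

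**What the plan says.** **Protocol, safety follow-up.** Section 9.2 states that "AEs will be followed until 30 days after the end of study/withdrawal" and adds that "Related SAEs will be recorded regardless of time from last dose". Section 9.5 states that "All SAEs will be followed to resolution". None of these sentences refers to a further consent.

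**Protocol, consent after withdrawal.** Section 6.3.1: "In the case of withdrawal, separate consent will be sought to allow the continued collection on patient status".

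**Protocol, OS.** Section 8.1: "Patients without a death date will be censored at the date the patient was last known to be alive". Consent does not enter this rule.

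**SAP 10, sources of death.** A death on study is the completion date on CRF page 18; "if after withdrawal from the study, the date of death recorded on the Post-study CRF" is used. The AE form is not named as a source. A further sentence brings a withdrawn patient's death into the analysis on condition that the patient consented.

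**SAP 10, censoring.** "Patients withdrawing from the study without consent for further follow up will be censored for survival at the date of their withdrawal", as recorded on CRF page 18. No exception is made for a death known from another record.

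**SAP 11** reports one departure for OS: the time origin is Day 0 and not enrolment. It does not mention the censoring rule.

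**The concern.** Two parts of the plan cover the same days after withdrawal and treat them differently. The safety rules keep collecting, so a fatal outcome can reach the AE data. The OS rules stop at withdrawal unless a second consent was signed. A death date held on an AE or SAE form makes the patient an event under Protocol 8.1 and a censored patient under SAP 10.

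The withdrawal rule may cover many patients. Listing 1 allows only death or withdrawal as off-study status and notes that the trial was terminated in December 2018, so patients alive at termination would also be coded as withdrawn.

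At stake are the death count, the survival percentiles and the curve in a very small cohort, and the agreement of the OS output with the AE listing in the same report. Withdrawal for an AE followed soon by death is also a setting in which censoring is likely to be informative.

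**Working it through.** The plan states no sample size, event count or power (Protocol 10.2 and 10.3 read N/A), so there is no figure to reproduce. The check compares the texts and then illustrates the size.

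**1. The overlap.** Take a patient who withdraws on day W, gives no post-study consent, and dies on W + 10 of an AE under follow-up.
- Protocol 9.2 and 9.5: the fatal outcome falls within AE follow-up. The Listing 12 shell has outcome and end-date columns, and its intensity code includes 5 for death.
- Protocol 8.1: a death date exists, so the patient is an event.
- SAP 10: no page 18 death and no Post-study CRF, so the patient is censored at W in Table 8 and Figure 2.
- The SAP has no step that compares fatal AE outcomes with the OS data.

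**2. Which deaths are affected.** Protocol 9.1.1.7 leaves progression deaths out of the fatal SAE criterion. Protocol 9.1.1.8 captures them only when progression was faster than expected. The gap therefore mainly concerns non-progression deaths, faster-than-expected progression deaths and other fatal SAEs.

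**3. Cohort size (assumed).** Protocol 4.2 gives 18 eligible completers, of whom 3 had died, 1 stopped for pregnancy and 2 stopped for unknown reasons by August 2011: 18 − 3 − 1 − 2 = 12. This assumes that all 18 continued on named-patient supply and that the six are among them. The SAP's 2×5 panel plots suggest 10. An outer bound is 18 − 3 = 15.

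**4. Effect of one death.** Let n patients have d deaths, with no other censoring before the last death. The final Kaplan-Meier estimate is (n − d)/n. If the j-th death is instead censored just before it occurs, the estimate becomes

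[(n − j + 1)/n] × [(n − d)/(n − j)].

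This is smallest at j = 1, where it equals (n − d)/(n − 1), and largest at j = d, where it equals (n − d + 1)/n. The death counts are assumed.

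| n | d | All deaths counted | First death censored | Last death censored | Difference (points) |
|---|---|---|---|---|---|
| 12 | 6 | 6/12 = 50.0% | 6/11 = 54.5% | 7/12 = 58.3% | 4.5 to 8.3 |
| 10 | 4 | 6/10 = 60.0% | 6/9 = 66.7% | 7/10 = 70.0% | 6.7 to 10.0 |
| 15 | 7 | 8/15 = 53.3% | 8/14 = 57.1% | 9/15 = 60.0% | 3.8 to 6.7 |

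**5. A hypothetical set of 10.** Suppose deaths at 1.0, 1.8, 3.0 and 4.5 years, and a fifth patient who withdraws at 2.0 and dies at 2.05; the other five are censored from 5.5 years on. Under SAP 10 the estimate at 4.5 years is 0.9 × 8/9 × 6/7 × 5/6 = 57.1%. With the death counted it is 0.9 × 8/9 × 7/8 × 6/7 × 5/6 = 50.0%. The curve first reaches 75% or below at 2.05 instead of 3.0 years. It reaches 50% at 4.5 years instead of not at all.

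**6. Survivors.** Moving a survivor's censoring date by 30 days adds 30/365.25 = 0.08 years. What matters is the missed event, not the censoring time.

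**The case against.** **The SAP can be read more kindly.** The censoring text in SAP 10 opens with patients who are still alive, and the disputed sentence stands in a paragraph about patients who lack a death date. On that reading a known death is never censored and the SAP agrees with Protocol 8.1. This carries some weight, but SAP 10 also makes a death after withdrawal count only if consent was given and names only two sources of death dates. At best the text is ambiguous.

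**Consent.** Whether a patient is alive is patient status, which is what the separate consent covers. The consent form is not available, and the protocol does not say whether AE follow-up continues after full withdrawal of consent. This stands, so any fix has to be limited by the consent given.

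**The death date.** The Listing 12 shell has an end date but no date-of-death field, unlike Listing 17. A usable date in the AE data is likely but not shown.

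**Importance.** SAP 4 makes no inferential claim, Protocol 3.4 says the study is not meant to provide evidence of efficacy, and full patient listings would let a careful reader find a mismatch. This lowers the severity.

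**Stronger readings that the documents do not support.** A reader might infer that recorded deaths have been discarded; no such death appears in either document. A reader might say that the patient is analysed as alive; in fact the patient leaves the risk set on a date when known to be alive. A reader might expect Table 10f and Table 8 to disagree on who died. Table 10f pools AEs leading to withdrawal with those leading to death and gives no count of deaths, so only Listing 12 would reveal the difference. That such patients are less likely to sign a second consent is plausible but undocumented.

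**Conclusion.** The point holds as a conditional gap in SAP 10. The SAP adds a consent condition to OS that Protocol 8.1 does not have, does not disclose it in SAP 11, and does not connect post-withdrawal AE outcomes to OS. If a non-consenting withdrawn patient had a fatal AE recorded in follow-up, OS would miss it and the curve would lie too high: by roughly 5 to 10 points at its end for one death among 10 to 12 patients, or about 4 to 7 points with 15. If no such death occurs, OS loses no event.

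These sizes rest on assumed numbers of patients and deaths and on no other censoring before the last death. The comparison uses the protocol as supplied, whose amendment summary ends at 7.0; SAP 1 cites version 9.0 with amendments up to 8.0. The gap is worth correcting because one death matters at this size, but it is not evidence that the reported OS is biased.

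**What to change.** Replace the consent-dependent censoring text in SAP 10 with a rule to this effect:

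- Within the limits of the consent given, a death validly recorded in any study record (CRF page 18, AE/SAE form or Post-study CRF) up to the end of the 30-day AE follow-up is an event at its date.
- A withdrawn patient without post-study consent and with no recorded death is censored at the last date known alive, up to that same 30-day limit.
- A death in a non-consenting patient learned later, only through SAE follow-up, is listed separately and not counted in Table 8. SAE follow-up has no time limit, whereas survivors are contacted only to 30 days; counting these late deaths would ascertain deaths over a longer window than survivors and push OS down.

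Patients with post-study consent stay under the existing rule. Before the final tables, reconcile fatal AE outcomes and their dates with CRF page 18 and the Post-study CRF. State the departure from Protocol 8.1 and its reason in SAP 11. If consent bars this use of the safety data, say so and report how many patients are affected.

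The cost is one SAP paragraph, a check of consent wording and a cross-check of existing records, with no new visits. The downside is that OS may look slightly less favourable.

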Eighteen patients (95%) reported at least one treatment-emergent AE after receiving IMM-101. Over the course of the study, a total of 119 treatment-emergent AEs were reported. There were 86 reports of treatment-emergent AEs that would be accepted as typical of a post-vaccination state (such as injection site reactions, joint pains/aches, headaches and flu-like symptoms) occurring at all dose levels. These were mainly mild in intensity, mostly resolved in a matter of days and responded well to simple supportive medication (e.g. paracetamol). They were entirely consistent with the pooled information available on *M. vaccae*, a closely related organism, and were generally less intense than symptoms typically observed following Bacille Calmette-Guérin (BCG) vaccination of tuberculin negative individuals.

Sixteen patients (84%) reported at least one treatment-related AE. A total of 56 treatment-related events were reported; the most frequently reported treatment-related adverse events were in the ‘administration site conditions’ category. All these injection reactions (local swelling, pain, erythema and occasionally mild ulceration) were considered ‘non-serious’ by the Investigator; no patient withdrew due to an intolerable injection site reaction.

Only one serious adverse event (SAE) was reported; one patient in the IMM-101 0.5 mg group was hospitalised with progressive shortness of breath and found to have progressive disease (metastatic lung lesion). The SAE was reported to be unrelated to IMM-101 by the Investigator.

The data collected at site to document and characterise injection site reactions indicated a trend for resolution over time, with the earlier and older skin reactions appearing reduced in size compared to the more recent ones at the end of the study. Furthermore, it appears that repeated administration does not predispose the patient towards larger or more intense reactions after subsequent administrations.

In summary, the study was conducted per protocol and provided considerable knowledge concerning the administration of IMM-101 and management of any side-effects. The AEs observed so far with IMM-101 are in line with expectations, are manageable and are in keeping with data from non-clinical models and past experience in humans with similar whole cell mycobacterial preparations. The injection site reactions are consistent for this

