#### ***9.1.1.4 Intensity of Adverse Events***

All AEs (or toxicities) including local injection site reactions encountered during the study will be evaluated according to the NCI CTCAE v4.0 [5] grading system (0 to 5), where applicable.

Grade	Description
1	Mild; asymptomatic or mild symptoms; clinical or diagnostic observations only; intervention not indicated.
2	Moderate; minimal, local or non-invasive intervention indicated; limiting age-appropriate instrumental activities of daily living.
3	Severe or medically significant but not immediately life-threatening; hospitalisation or prolongation of hospitalisation indicated; disabling limiting self care activities of daily living.

CONFIDENTIAL

Immudulon Therapeutics Ltd.  
[name]

- 4 Life-threatening consequences; urgent intervention indicated.
- 5 Death related to AE.

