### **9.4 *RECORDING AND REPORTING ADVERSE EVENT/INTERCURRENT ILLNESSES***

It is the responsibility of the Investigator to document all AEs that occur during the study from patient entry. An AE includes any noxious, pathological or unintended change in anatomical, physiological or metabolic functions as indicated by physical signs, symptoms and/or laboratory changes whether or not associated with the study drug and whether or not considered related to the study drug. This includes an exacerbation of pre-existing conditions or events, intercurrent illnesses or drug interaction. Anticipated day-to-day fluctuations of pre-existing conditions that do not represent a clinically significant exacerbation or worsening need not be considered AEs.

Patient entry into the study is defined as the time at which informed consent is obtained (this must be before any Protocol-specific diagnostic procedures or interventions). All subsequent AEs must be reported regardless of whether or not they are considered drug related.

Adverse events will be elicited by asking the patient a non-leading question, for example “Have you experienced or are you experiencing any new or changed symptoms since we last asked/since your last visit?” Adverse events should be reported on the appropriate page of the CRF.

Each AE will be assigned a CTCAE severity/intensity category as described in Section 9.1.1.4. Further details can be found at the following website:

[http://ctep.cancer.gov/protocolDevelopment/electronic\\_applications/docs/ctcaev3.pdf](http://ctep.cancer.gov/protocolDevelopment/electronic_applications/docs/ctcaev3.pdf)

If there is a change in severity of an AE, it must be recorded as a separate event.

Every effort should be made by the Investigator to explain each AE and assess its relationship, if any, to study drug treatment. Causality should be assessed using the categories as described in Section 9.1.1.3.

The Investigator must report in detail all adverse signs and symptoms which are either volunteered by patients or observed during or following the course of investigational product administration on the appropriate CRF page.

In the event of a SAE/SUSAR, the Investigator will notify Emas within 24 hours:

SAE CONTACT DETAILS: Emas Ltd.  
[name]  
[contact]  
[contact]  
Email: [[contact]](mailto:[contact])

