#### 10.1.1.2 *Other Safety Endpoints*

##### Injection Site Reactions

The frequency and severity of injection site reactions will be summarised.

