- Treatment emergent, IMM-101-related, adverse events: AEs that are definitely, probably or possibly related to study drug or with an unknown relationship (Table 10d)
- Treatment emergent, SAEs (Table 10e)
- Treatment emergent adverse events leading to withdrawal or death (Table 10f).
- Treatment emergent non-serious adverse events (Table 10g).

Additionally, long term safety will be evaluated by combining treatment related adverse event experience in the FIH study through to the end of the LTF study by summarising treatment emergent treatment-related adverse events (IMM-101-001 and IMM-101-008 Combined) (Table 10h).

Where it is not applicable to grade an AE using NCI CTCAE grade, it will be excluded from the summary of NCI Grade 3 and above AEs. Any AEs with missing grades, however, will be included, based on a worst-case approach.

On-study injection site reactions are summarised over the treatment period by visit in Table 11.

Urine Pregnancy Test Results and blood samples for immunological markers will be listed but not summarised.

All safety data will be listed.

Any comments recorded as free text in the CRF will be listed.

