Unique Patient ID	Visit Name/ Number	Visit Date (DD-MM-YYYY)	Date Last Dose of IMM-101 Administered (DD-MM-YYYY)	Is/are Injection Site Reaction(s) Visible From Previous Doses(s) of IMM-101?	Do(es) the Local Reaction(s) Affect Daily Activities?	Are Injection Site Reactions Becoming More Troublesome With Repeated Doses of IMM-101	Wound Care Required	Description of Wound Care Provided
xxxxxx	xxxxxx	DD-MM-YYYY	DD-MM-YYYY	xxxxxx	xxxxxx	xxxxxx	xxx	xxxxxx
xxxxxx	xxxxxx	DD-MM-YYYY	DD-MM-YYYY	xxxxxx	xxxxxx	xxxxxx	xxx	xxxxxx
xxxxxx	xxxxxx	DD-MM-YYYY	DD-MM-YYYY	xxxxxx	xxxxxx	xxxxxx	xxx	xxxxxx
xxxxxx	xxxxxx	DD-MM-YYYY	DD-MM-YYYY	xxxxxx	xxxxxx	xxxxxx	xxx	xxxxxx
xxxxxx	xxxxxx	DD-MM-YYYY	DD-MM-YYYY	xxxxxx	xxxxxx	xxxxxx	xxx	xxxxxx
xxxxxx	xxxxxx	DD-MM-YYYY	DD-MM-YYYY	xxxxxx	xxxxxx	xxxxxx	xxx	xxxxxx
xxxxxx	xxxxxx	DD-MM-YYYY	DD-MM-YYYY	xxxxxx	xxxxxx	xxxxxx	xxx	xxxxxx
xxxxxx	xxxxxx	DD-MM-YYYY	DD-MM-YYYY	xxxxxx	xxxxxx	xxxxxx	xxx	xxxxxx

Code: S:\Services\Immodulon\IMM-101-008\Analysis\Development\Code\Listing13.sas ddmmmyy:hh:mm:ss

Data: S:\Services\Immodulon\IMM-101-008\xxxx.sas7bdat

Note to programmer: Please update data footnote with appropriate file directory.**Note to programmer:** Visit Name/Number should be one of Screening, Day 0 or Routine Visit xx.

CONFIDENTIAL**Exploristics Limited**

Identifier: EXP12002

Clinical Study Identifier: IMM-101-008

Final Analysis

Protocol: IMM-101-008

Analysis Population: Safety Population

Page x of y

Listing 14
Concomitant Medication and Adverse Event Checks

Unique Patient ID	Visit Name/Number	Visit Date (DD-MM-YYYY)	Any medication (prescription or non-prescription) started or ceased since the last dose of IMM-101? (Y/N/Unknown)	Other than a local reaction, did the patient have any concurrent sign(s), symptoms(s), and/or disease(s)? (Y/N)
xxxxxx	xx	DD-MM-YYYY	xxxxxx	xxxxxx
xxxxxx	xx	DD-MM-YYYY	xxxxxx	xxxxxx
xxxxxx	xx	DD-MM-YYYY	xxxxxx	xxxxxx
xxxxxx	xx	DD-MM-YYYY	xxxxxx	xxxxxx
xxxxxx	xx	DD-MM-YYYY	xxxxxx	xxxxxx
xxxxxx	xx	DD-MM-YYYY	xxxxxx	xxxxxx
xxxxxx	xx	DD-MM-YYYY	xxxxxx	xxxxxx
xxxxxx	xx	DD-MM-YYYY	xxxxxx	xxxxxx

Note: UK, U = Unknown.

Code: S:\Services\Immodulon\IMM-101-008\Analysis\Development\Code\Listing14.sas ddmmmyy:hh:mm:ss

Data: S:\Services\Immodulon\IMM-101-008\xxxxxx.sas7bdat

Note to programmer: Please update data footnote with appropriate file directory.**Note to programmer:** Visit Name/Number should be one of Screening, Day 0 or Routine Visit xx.

CONFIDENTIAL**Exploristics Limited**

Identifier: EXP12002

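### Injection site reactions become AEs only at the investigator's discretion and have no CTCAE field in the local-reaction displays, so the AE tables may under-count them and pooled Table 10h may mix recording rules

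*Protocol*

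**What the plan says.** Two protocol sections leave AE entry to judgement. Section 9.1.3.1 says that "an injection site reaction may be recorded as an AE at any time if considered appropriate to do so by the Investigator", and section 9.2 says of reactions assessed before each injection: "These will only be recorded as an AE if deemed appropriate by the Investigator". Neither gives a threshold. The visit-level AE check shown in SAP Listing 14 steps around local reactions: "Other than a local reaction, did the patient have any concurrent sign(s), symptoms(s), and/or disease(s".

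Other sections point the other way. Section 9.1.1.4 says "All AEs (or toxicities) including local injection site reactions encountered during the study will be evaluated according to the NCI CTCAE v4.0", qualified by a where-applicable clause. Section 9.4 says "The Investigator must report in detail all adverse signs and symptoms which are either volunteered by patients or observed during or following the course" of administration.

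On reporting, protocol section 10.1.1.1 and SAP section 4 promise local toxicities by number, degree and type. Protocol section 10.1.1.2 adds: "The frequency and severity of injection site reactions will be summarised". The SAP meets this with Table 11 (by visit) and Listing 13. SAP section 9.3 also introduces Table 10h, which evaluates long-term safety by "combining treatment related adverse event experience in the FIH study through to the end of the LTF study".

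**The concern.** Protocol section 3.4 calls injection site reactions the main risk of the product, and section 9.1 makes local toxicity part of the primary objective. Tables 10a (overview), 10c (Grade 3 and above), 10d (related) and 10h (related, both studies) are built from AE records. If a reaction is left out of the AE data because it was expected, those tables show less local toxicity than occurred, and a reader cannot separate tolerability from a recording habit.

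Table 10h has a further difficulty. In Phase I, administration-site conditions were the most frequent category of related AE (protocol section 3.3). Table 10h adds those events to follow-up events that have passed through the discretionary rule, in one column with no split and no footnote.

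**Working it through.** **1. The Phase I figures.** These are the only numerical benchmark, since the study states no sample size, alpha or power. Patients with a related AE: 16/19 = 84.2% (stated as 84%). Patients with any treatment-emergent AE: 18/19 = 94.7% (stated as 95%). IMM-101 injections: 6×3 + 6×3 + 6×3 + 1×2 = 56. Section 3.3 reports: "A total of 56 treatment-related events were reported". That is 56/56 = 1.0 related AE per injection. The local share of the 56 is not stated.

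**2. Following one reaction.** Take a reaction seen at a follow-up visit that the investigator does not consider an AE.

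| Place | What happens to it |
|---|---|
| Protocol 9.1.1.4 | Should be evaluated by CTCAE |
| Protocol 9.4 | Should be reported as an observed adverse sign |
| Protocol 9.1.3.1, 9.2 | Need not be an AE |
| Listing 14 check | Not asked about |
| Table 11, Listing 13 | Visibility, effect on daily activities, worsening, wound care; no CTCAE grade |
| Listing 12 (the only listing with CTCAE intensity) | Absent, because not an AE |
| Tables 10a, 10c, 10d, 10h | Absent |

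The worst-case rule in SAP section 9.3, which puts AEs with a missing grade into the Grade 3 and above summary, cannot reach a reaction that was never entered as an AE.

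**3. Direction.** Let r be the probability that a reaction is entered as an AE. The expected share of reaction events in the AE tables is r, which cannot exceed 1. A patient with k reactions appears with probability 1 − (1 − r)^k, taking entries as independent. The documents do not give r; these values are assumptions.

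| r | Events shown | Patients shown, k = 1 / 2 / 3 |
|---|---|---|
| 1 | 100% | 100% / 100% / 100% |
| 0.5 | 50% | 50% / 75% / 87.5% |
| 0.25 | 25% | 25% / 43.8% / 57.8% |

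One year of dosing every 4 weeks is 52/4 = 13 injections. With 13 reactions and r = 0.25, the patient share is 97.6%. Event counts therefore suffer more than patient counts.

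**4. What this could do to Table 10c.** The follow-up N is not stated. Protocol section 4.2 implies 18 − (3 + 1 + 2) = 12 still on treatment in August 2011; 10 is shown as a lower value. Assume that 20% of patients truly have one Grade 3 or higher reaction. Expected patients shown = N × 0.2 × r, and the chance that none is shown = (1 − 0.2r)^N.

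| r | N = 12: expected; chance of none | N = 10: expected; chance of none |
|---|---|---|
| 1 | 2.4; 6.9% | 2.0; 10.7% |
| 0.5 | 1.2; 28.2% | 1.0; 34.9% |
| 0.25 | 0.6; 54.0% | 0.5; 59.9% |

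This shows sensitivity to r and estimates nothing. A severe reaction is probably more likely than a mild one to be entered, so r for this table may be nearer 1.

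**The case against.** The strongest reply is that local reactions are not lost. SAP section 2.2 lists local injection site tolerability as its own endpoint. Table 11 and Listing 13 report the reactions assessed at visits, on a five-level scale from no effect to intolerable, with items on worsening and wound care. Since CTCAE Grades 2 and 3 are themselves defined partly by limits on daily living, that scale does measure severity. The exclusion in Listing 14 is consistent with sending local reactions to a dedicated form. Other routes into the AE data also remain: section 9.4, the SAE criteria, and section 9.1.1.9, which classes events leading to dose reduction or withdrawal as significant AEs.

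Most of this stands, and it limits the point to the AE tables. It does not supply a CTCAE grade or reaction type in Table 11. Nor does it cover a reaction reported by telephone: protocol section 5.2 sends AE and medication details from the call to the CRF but does not say the same of reactions.

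A second reply is that different recording rules are not proven. The Phase I protocol and CRF are not in the documents. Section 3.3 says that separate data on reactions were collected then too, and 19 − 16 = 3 patients had no related AE although skin reactions were expected. Phase I may have used the same discretion. That stands: comparability is not shown, in either direction.

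Third, the SAP cites protocol version 9.0 with amendments to 8.0, while the amendment log in the protocol reviewed ends at 7.0. The wording of section 9.2 should be checked against version 9.0.

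**Conclusion.** The point holds as an inconsistency with a one-sided risk. The protocol sections conflict on whether a local reaction must be graded and reported; the SAP's reaction displays cannot show a CTCAE grade; and the four AE tables can under-count local reactions but not over-count them through this rule. The size depends on r and ranges from no effect to omission of most reaction events.

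Three stronger readings are tempting and are not supported:

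- **Reactions outside the AE data go ungraded.** Section 9.1.1.4 calls for CTCAE evaluation, and the Grade 3 threshold in section 9.1.3.1 presupposes a grade. The CRF was not available, so only the absence of a grade from the planned displays is shown.
- **Table 10h will make local toxicity appear to fade with extended use.** Its shell is a single combined column with no period split and no rate per dose, so it displays no trend. Worsening with repeated doses is addressed by visit in Table 11.
- **The related-AE rate would fall from 1.0 to between 0.5 and 0.1 per injection.** This needs an assumed local share of 50–90% and no local reaction ever entered as an AE. It is a worst case. Its base is also all 19 Phase I patients, whereas Table 10h covers only those who entered follow-up.

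**What to change.** **In the SAP, with data already held.** In Tables 10d and 10h, show administration-site events as a block separate from other related AEs, and split 10h by study. Footnote Tables 10a, 10c, 10d and 10h to say that follow-up reactions were entered as AEs only at investigator discretion, and refer the reader to Table 11 for the local result. Add to Table 11 an overall summary of each patient's worst daily-activities category, plus any CTCAE grade that was recorded.

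**In the protocol or any successor study.** Reconcile sections 9.1.1.4, 9.1.3.1, 9.2 and 9.4 so that every assessed reaction gets a CTCAE grade on the existing reaction form, under one stated rule for AE entry. Align the AE prompt with that rule. This cannot recover data here: Listing 1 notes that the trial was terminated in December 2018, before the SAP amendment took effect in April 2019.

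**Cost.** Separate blocks in two tables with one split by study, some footnotes, a short addition to Table 11 and, for a future study, one form field. The tables may look slightly less favourable.
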